11/20/2023

[figure not shown]
Dear FDA Clinical Trials Review Board,

Please find attached the *study protocol and statistical analysis plan* document as requested on the PRS System.

This is for the study: *Intracanalicular Dexamethasone Insert for Post-Corneal Cross-Linking Inflammation and Pain- The LINK Study* (IND 146603; NCT04168112)

Please do not hesitate to contact me with any questions or concerns regarding this document.
Thank you for your time and consideration.

Sincerely,

[name], DO
SightMD
[name]
[name]
[contact]

*Intracanalicular Dexamethasone Insert for Post-Corneal Cross-Linking Inflammation and Pain-
The LINK Study*

Protocol in brief: This prospective, open-label, single-center, randomized, investigator-sponsored clinical study sought to investigate the efficacy of dexamethasone intracanalicular insert on post-corneal crosslinking inflammation and pain in keratoconus patients. This study planned to enroll 20 patients and follow patients over the course of several study visits [(postoperative day (POD) 1, POD-3, POD4-7, POW2, POW3 and POW4]. It is anticipated that corneal re-epithelialization will occur within the first postoperative week, but patients were be followed closely for documentation of therapeutic effect for 30 days due to duration of steroid therapy (i.e. dexamethasone intracanalicular insert or use of Prednisolone acetate 1% ophthalmic solution tapered over 1 month in the following schedule: 4 times daily x1 week, 3 times daily x 1 week, 2 times daily x 1 week, and daily x 1 week). All patients will receive postoperative fluoroquinolone antibiotic eye drops with instructions for use (i.e. 1 drop in operative eye 4 times daily x 10 days). All patients were evaluated for pain scores, rate of corneal re-epithelialization, ease of use of the post-crosslinking regimen, and need for rescue pain medication after standard bilateral epithelium-off crosslinking.

Biostatistics

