Study variables were analyzed by appropriate statistical methods to assess for the differences between eyes treated as an entire group, and as broken down between dexamethasone implant and traditional prednisolone drop groups. Correlations between ease of use, intraocular inflammation, and epithelial healing were assessed using χ^2 , t-test, Pearson, and the Fisher Z-transformation test, evaluating the sample correlation r for significance. For independent samples, the t-test or Mann-Whitney-U test will be used for scaled data based on the outcome of the Kolmogorov-Smirnov test for normality of distribution. Ordinal data was analyzed using the Mann-Whitney-U test and chi-square or Fisher's Exact test for nominal data. P-values less than or equal to 0.05 were considered statistically significant. For non-inferiority or equivalency data, 95% confidence intervals were formulated and compared with equivalency margins. Sample size is small secondary to the incidence of the disease (1:2,000)

For any patient deciding to withdraw from the follow-up, the reasons for the withdrawal were recorded for the subsequent analysis in the interpretation of the results. Reasons behind drop out were investigated and included in study results. The authors only analyzed complete cases, as imputing the missing data using single or multiple imputation methods would be confounded by the small sample size. ITT for ease of use was calculated utilizing extremely conservative estimates of a 70% +/- 10% for drops and 90% for dexamethasone insert, while utilizing a two independent sample study with a continuous endpoint, 1:1 enrollment ratio, alpha/beta of 0.05, and power of 95%. We calculated the minimum number of patients needed to enroll as 12.

In order to account for type I errors over multiple endpoints Bonferroni adjustment method was utilized.

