Central corneal pachymetry (CCT) will often change over the course of post-CXL healing and as such was assessed at baseline and at the completion of the study between groups. As expected, there was no significant difference in mean CCT between groups at baseline (505.4 ± 47.6 μ m in prednisolone group and 509 ± 44.11 μ m in dexamethasone group), nor at POW4 (459 ± 33.89 μ m in prednisolone group; 473.15 ± 43.78 μ m in dexamethasone group).

At the end of the study, the patients were asked to complete an “ease of use” questionnaire regarding postoperative medications. The first question asked “Were directions regarding eye drop use post-CXL easy to follow”? All patients in both groups responded “yes” to this. The second question asked, “Was it cumbersome to use eye drops for more than 10 days” (this pertained to the prednisolone group), however 100% responded “no”. The final question asked “Was it difficult to remember to use postoperative drops?”; 100% of patients responded “no”. No patient experienced any adverse results in relation to treatment or CXL.

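### The trial was sized on a continuous drops-versus-insert ease-of-use score, but the three reported questionnaire items are yes/no, ask only about eye drops, and do not measure that endpoint

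*Combined protocol and SAP*

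**What the plan says.** **Sizing (Biostatistics).** Ease of use is the only outcome with a stated sample-size basis: "ITT for ease of use was calculated utilizing extremely conservative estimates of a 70% +/- 10% for drops and 90% for dexamethasone insert". The calculation is for a "two independent sample study with a continuous endpoint", with "1:1 enrollment ratio, alpha/beta of 0.05, and power of 95" percent, and ends: "We calculated the minimum number of patients needed to enroll as 12". The planned enrolment in Protocol in brief is larger: "This study planned to enroll 20 patients".

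**Outcome and regimen (Protocol in brief).** Ease of use of the postoperative regimen is one of four listed evaluations, beside pain scores, re-epithelialization and rescue pain medication. The prednisolone arm has a four-week taper. Drops are not confined to that arm: "All patients will receive postoperative fluoroquinolone antibiotic eye drops with instructions for use", four times daily for 10 days.

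**Instrument (results narrative, closing paragraph).** Three items were given at the end of the study, introduced as first, second and final:

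1. Whether the eye-drop directions were easy to follow. Everyone in both groups said yes.
2. Whether using drops for more than 10 days was cumbersome. The text adds "this pertained to the prednisolone group), however 100% responded" no.
3. Whether it was hard to remember the drops. Everyone said no.

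**Planned analysis (Biostatistics).** "Correlations between ease of use, intraocular inflammation, and epithelial healing were assessed", using tests that include Pearson correlation.

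**The concern.** The sample size presupposes a numerical ease-of-use score in each arm, one for drops and one for the insert. The reported instrument gives no such score and never mentions the insert. A reader who sees 100% in both arms could conclude that the two regimens are equally easy, or that the insert has no convenience advantage over a contrast the trial was powered at 95% to detect. Neither conclusion is available if the items did not measure that contrast. What is at stake is the interpretation of the one endpoint that justifies the sample size.

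**Working it through.** **1. Reproduce the stated 12.** Inputs from Biostatistics: means 70 and 90, so a difference of 20 points; ± 10 read as a standard deviation and assumed common to both arms; alpha 0.05, with sidedness not stated; power 95%; 1:1 allocation. Normal approximation: n per arm = 2 × [SD × (z_alpha + z_beta) / difference]².

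- One-sided: 2 × [10 × (1.645 + 1.645) / 20]² = 5.41, so 6 per arm and **12 in total**.
- Two-sided: 2 × [10 × (1.960 + 1.645) / 20]² = 6.50, so 7 per arm and 14 in total.
- Solving with the t distribution: 7 per arm (14 in total) one-sided and 8 per arm (16 in total) two-sided.

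The stated figure reproduces with the one-sided normal formula. It therefore rests on a continuous drops-versus-insert score with a 20-point difference and a standard deviation of 10.

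**2. Set the items against that endpoint.**

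| Item | Response | Subject | Who answers | Assesses the insert or whole regimen? |
|---|---|---|---|---|
| 1 | yes/no | drop directions | both arms | no |
| 2 | yes/no | drops beyond 10 days | pertains to prednisolone arm | no |
| 3 | yes/no | remembering drops | both arms | no |

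Item 2 has no counterpart in the insert arm, where the only scheduled drops are the 10-day antibiotic.

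**3. What items 1 and 3 can contrast.** Drops per eye from the schedule in Protocol in brief, at one drop per prednisolone dose (assumed):

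- Prednisolone: 4×7 + 3×7 + 2×7 + 1×7 = 28 + 21 + 14 + 7 = 70.
- Antibiotic: 4 × 10 = 40, in both arms.
- Total: 70 + 40 = 110 in the prednisolone arm and 40 in the insert arm. The insert removes 70/110 = 64%.

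The two arms thus answer items 1 and 3 about different amounts of drop use. That is an indirect contrast in drop burden, on a yes/no scale.

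**4. Effect of the yes/no scale.** Suppose 70% and 90% were proportions giving the favourable answer.

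- Two-sided, 95% power, no continuity correction: [1.960 × √(2 × 0.8 × 0.2) + 1.645 × √(0.7 × 0.3 + 0.9 × 0.1)]² / 0.2² = (1.109 + 0.901)² / 0.04, or about **101 per arm** (111 with the correction).
- With 10 per arm (20 planned, 1:1, an assumption), power is about 19% by normal approximation and about **6%** by Fisher's exact test.
- On the continuous score, 10 per arm gives about 99% power, two-sided.

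**5. What unanimous answers allow.** With an assumed 10 per arm, 10/10 against 10/10 gives Fisher p = 1.0. The exact two-sided 95% lower limit for 10/10 is 0.025^(1/10) = 0.69. A Pearson correlation with a variable that never varies is 0/0, so the ease-of-use correlations cannot be estimated from these items.

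**The case against.** **Some information between arms.** A reader might infer that the questionnaire could not have shown any difference, because items 1 and 3 concern only the antibiotic that both arms share. The documents do not support that. Neither item is limited to antibiotics, and a prednisolone patient answers about antibiotic plus taper. A difference on item 3 could have reflected the burden the insert removes. This stands, and it limits the point to items that are indirect and coarse.

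**The unanimous result says something.** Every prednisolone patient found the longer course not cumbersome, and nobody found drops hard to remember. If 70% were a proportion, the chance of 10 favourable answers in 10 would be 0.7^10 = 2.8%. That is some evidence against a heavy drop burden on these items. It is only illustrative, because the plan treats 70% as the mean of a continuous score and the 10 per arm is assumed. It also says nothing about the experience of the insert.

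**Unanimity is a result.** The undefined correlation follows from the answers received and was not a flaw of the plan in advance. This stands. The results narrative also reports no ease-of-use correlation and claims no ease-of-use advantage for either arm.

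**Recall.** A reader might infer that insert patients were recalling drops stopped long before the questionnaire. The text gives its timing only as the end of the study, and nothing shows that recall affected a yes/no answer. The point does not rely on it.

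**Importance.** The title and stated aim concern inflammation and pain, and ease of use is never named primary. This stands and lowers the severity.

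**Conclusion.** The concern holds in a limited form. The sample size of 12 rests on a continuous ease-of-use difference of 20 points between drops and insert. The reported items are yes/no, concern drops only, and do not measure that difference. One of the three has no comparator. The other two contrast total drop burden indirectly, at about 110 against 40 drops per eye. On a yes/no scale, the assumed 70% and 90% would have had about 6% power by Fisher's exact test at 10 per arm. The 100% results therefore do not test the 70% versus 90% assumption.

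This should be corrected, but it does not threaten the rest of the trial: the pain, healing, intraocular pressure and pachymetry results do not depend on the questionnaire.

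The conclusion assumes that ± 10 is a common standard deviation, that 20 patients were split 10 and 10, that each prednisolone dose is one drop, and that the three items are the whole questionnaire. The narrative's numbering suggests they are, although part of the combined document was not available for review. A scored ease-of-use scale described there would change the finding.

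**What to change.** **For the data already collected:**

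- Report ease of use as descriptive only, item by item.
- State that the items did not directly assess the insert, the steroid component or the whole regimen, and do not test the 70% versus 90% contrast.
- Note in Biostatistics that the ease-of-use correlations are not estimable because all answers were the same.

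This costs a few sentences and changes no other result.

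**For any further use of the plan:**

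- Ask both arms the same scaled items, for example 0 to 100, on ease of the whole postoperative regimen and ease of the anti-inflammatory treatment received.
- Give them at visits already scheduled.
- Name the score on which the sample size is based. The t-test or Mann-Whitney comparison already provided for scaled data would then apply to it.

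The cost is slightly more questionnaire burden for patients and no extra visits. Because data collection is complete, this part cannot repair the present results.
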